3.5.2 Secondary endpoints

3.5.2.1 Acute procedural outcomes

- Procedure time (skin to skin)
- Radiofrequency time
- Number of applications (total/per RF line/per segment)
- Fluoroscopy time
- First-pass isolation rate
- Early PV reconnections

3.5.2.2 Peri-procedural complications

The following procedure-related complications will be collected:

- Death
- Myocardial infarction
- Diaphragmatic paralysis
- Stroke or transient ischemic attack (TIA)
- Other thromboembolic events
- Cardiac perforation or tamponade
- Vascular complications
- Prolonged or repeat hospitalization
- Heart block
- PV stenosis >70% (as measured by cardiac CT)
- Atrio-esophageal fistula
- Pericarditis requiring intervention
- Pneumothorax
- Pulmonary edema

3.6 Variables

3.6.1 Enrollment evaluation

A complete evaluation will be performed in each patient at enrollment, including:

1. Patient demographic data
2. Clinical evaluation with a physical examination
3. Medical and cardiovascular history
4. NYHA functional class
1. Medication list
2. 12-Lead ECG
3. Transthoracic echocardiography with
 - a. LA diameter
 - b. LVEF (biplane Simpson's method) (%)
4. Trans-esophageal echocardiography/Intra-cardiac echocardiography.

3.6.2 Procedural evaluation

5. MDCT wall thickness variables
 - 5.1. Mean LAWV (all of the atrial measures)
 - 5.2. Mean PVI RF line WT (only around the PV line)
 - 5.3. Normalized PVI RF line WT (point thickness/maximum PVI RF line thickness)
 - 5.4. Reconnection point mean WT (mean thickness on a 3mm radius around the point)
 - 5.5. Reconnection segment mean WT (mean thickness in each segment)
 - 5.6. Coefficient of variation of wall thickness on each segment (CV-WT) standard deviation of the wall thickness/mean WT
 - 5.7. Gaussian curvature (to have an idea of the heterogeneity of tissue)
6. Procedural data of the first PVI
 - 6.1. PV anatomy (presence or absence of common vein ostia)
 - 6.2. RF time
 - 6.3. Acute reconnection sites
7. Procedural data of the re-do intervention
 - 7.1. Reconnection sites according to an 8-segment model where the antral region of the PVs is divided into segments
 - 7.2. RF time
 - 7.3. EGM attenuation time

3.7 Follow-up

Clinical follow-up (FU) will include outpatient clinic visits at 3, 6 and 12 months after the ablation procedure. If no other contraindications, all antiarrhythmic drugs should be stopped at the 3-month FU visit (end of the 'blinking period'; see 'Outcomes' section before). 12-lead ECG and 24-hour ambulatory Holter monitoring will be performed in every scheduled

appointment. Successful ablation will be defined as the absence of clinical symptoms suggestive of AF recurrence, as well as the absence of documented AF in ECGs and/or Holter.

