3.5 Outcomes

3.5.1 Primary endpoint

The primary endpoint will be survival free of any atrial arrhythmia at 1-year follow-up. From this endpoint, important definitions must be taken into account:

- AF recurrence will be considered only after the 3-month ‘blinking period’ (see below), whenever the patient refers clear symptoms of recurrence (fast, recurrent palpitations with abrupt onset and termination, lasting for several minutes or hours), if AF is documented in an electrocardiogram (ECG), or whether it is recorded in a Holter registry (> 30 seconds).
- The ‘blinking period’ refers to the first 3-month period after the PVI procedure, where a transient increased risk of post-procedural atrial tachyarrhythmias is expected to occur due to pro-arrhythmogenic inflammatory changes after creating tissue RF lesions.

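### Section 3.7 defines successful ablation without the blanking period or the 30-second Holter threshold of 3.5.1, and no passage says which definition prevails

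*Combined protocol and SAP*

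**What the plan says.** **Section 3.5.1 (primary endpoint).** The endpoint is one-year survival free of any atrial arrhythmia. The attached definition begins "AF recurrence will be considered only after the 3-month" blanking period (printed as the blinking period), which "refers to the first 3-month period after the PVI procedure". A recurrence then needs one of three things:

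- symptoms, "whenever the patient refers clear symptoms of recurrence", with a listed character and duration;
- AF on an ECG;
- AF on Holter, "or whether it is recorded in a Holter registry (> 30 seconds".

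**Section 3.7 (follow-up).** "Successful ablation will be defined as the absence of clinical symptoms suggestive of AF recurrence, as well as the absence of documented AF". The documentation part reads in full "the absence of documented AF in ECGs and/or Holter". The paragraph does mention the blanking period and points back to the outcomes section, but only to time the stop of antiarrhythmic drugs.

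**Recordings.** Section 3.7 says "12-lead ECG and 24-hour ambulatory Holter monitoring will be performed in every scheduled" appointment and lists visits at 3, 6 and 12 months. The table in 3.8 has ECG and Holter at 1, 6 and 12 months.

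**Section 3.11.1 (sample size).** The 10% margin is placed on clinical success, explained in brackets as arrhythmia-free survival one year after the procedure. The blanking rule is not repeated there.

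**The concern.** The protocol holds two operational rules for what looks like the same result, and they classify some patients differently. These patients are to be expected: 3.5.1 itself explains that early arrhythmia is anticipated, and both visit schedules put an ECG and a Holter inside the blanking period (month 1) or at its edge (month 3).

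The study has a single arm and is judged against an external rate. A change of definition moves the observed rate directly, and no concurrent control group moves with it. If the definition is still open when the data are seen, the choice between two success rates could be made with the results in view.

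**Working it through.** **1. The two rules side by side**

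| Element | 3.5.1, recurrence | 3.7, success |
|---|---|---|
| Start of counting | after month 3 | none stated |
| Symptoms | clear, with a listed pattern | suggestive of AF recurrence, no pattern |
| AF on ECG | counts after month 3 | must be absent, no window |
| AF on Holter | more than 30 seconds | must be absent, no duration |
| Arrhythmia named | AF only (endpoint: any atrial arrhythmia) | AF only |

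**2. Test patients**

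- AF on the month-1 ECG and nothing later: no recurrence under 3.5.1; not a success under 3.7.
- A 20-second run of AF on the month-6 Holter and nothing else: no recurrence under 3.5.1; not a success under 3.7.
- Symptoms only, in month 2: no recurrence under 3.5.1; arguable under 3.7, because that sentence uses the term AF recurrence, which 3.5.1 restricts to after month 3.

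The first two follow from the text alone. The third does not.

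**3. How far the rate could move (illustration)**

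The plan gives no figure to reproduce on this point. Inputs:

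- Reference rate 91.3%, the CLOSE figure in the introduction, taken here as the true success rate under 3.5.1 (assumption).
- b, the share of those successful patients who have events only during blanking. The documents give no value, so a range is shown.

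Success under 3.7 = 91.3% x (1 - b):

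- b = 5%: 0.913 x 0.95 = 86.7%
- b = 10%: 0.913 x 0.90 = 82.2%
- b = 20%: 0.913 x 0.80 = 73.0%

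The rate falls 5 points below 91.3% at b = 1 - 0.863/0.913 = 5.5%, and 10 points below at b = 1 - 0.813/0.913 = 11.0%.

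**4. What that would do to the test, if 3.7 were the rule applied**

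Assumptions: 106 less 10% drop-out leaves 95 evaluable; a fixed threshold; an exact one-sided 5% binomial test. Section 3.11.1 gives both a 10% margin and a limit of -0.05, so both are shown.

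| b | Rate under 3.7 | Power, threshold 81.3% (at least 84 of 95) | Power, threshold 86.3% (at least 88 of 95) |
|---|---|---|---|
| 0 | 91.3% | 0.88 | 0.41 |
| 2% | 89.5% | 0.70 | 0.21 |
| 5% | 86.7% | 0.38 | 0.05 |
| 10% | 82.2% | 0.07 | 0.003 |

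In patients: 95 x 0.913 = 86.7 expected successes. At b = 5%, 86.7 x 0.05 = 4.3 of them are reclassified, leaving 82.4, which is below the 84 required at the 81.3% threshold.

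**The case against.** The strongest reply is that 3.5.1 governs. It names the primary endpoint and attaches the definitions that go with it. Section 3.11.1 explains clinical success as arrhythmia-free survival at one year, and 3.11.2 analyses the primary endpoint under the same description. Section 3.7 is about follow-up and never calls its success definition the primary endpoint. This largely stands: applying blanking is the likely intent. What remains is that 3.7 is worded as a definition, success is also the term on which 3.11.1 places the margin, and no sentence ranks the two.

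The reply also has force on symptoms. Because 3.7 speaks of AF recurrence, a reader may carry the blanking rule across. It does not reach documented AF, where 3.7 does not use that term.

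Three stronger readings are tempting, and the documents do not support them:

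- *That vague palpitations at, say, month 8 would fail 3.7 but pass 3.5.1.* This presumes that vague symptoms are suggestive ones. The wording in 3.7 may be shorthand for the pattern in 3.5.1.
- *That the primary analysis has two definitions of equal standing, so the non-inferiority result hangs on the choice.* Sections 3.5.1, 3.11.1 and 3.11.2 all point to the former definition. The figures above matter only if 3.7 displaces it.
- *That the month-3 recording makes the endpoint depend on the booking date, so blanking should end at the visit.* Any fixed cut-off separates neighbouring days, and time since ablation is a clear rule. Ending blanking at the visit would itself create dependence on booking and would discard AF recorded after month 3.

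**Conclusion.** The inconsistency is real and follows from the text. It is firm for documented AF confined to months 0 to 3 and for later Holter AF of 30 seconds or less. It is weaker for symptoms, where the wording is looser but can be read as consistent.

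Its size cannot be derived from the documents. The rates and power values show sensitivity to an assumed b. They also assume that 91.3% holds under 3.5.1, a fixed threshold, 95 evaluable patients and, above all, that 3.7 is the rule applied. They do not show that the trial's conclusion will change. They do show that a few reclassified patients would matter, which is reason enough to settle the definition before analysis.

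**What to change.** 1. Replace the success sentence in 3.7 with: *Success is the absence of any recurrence as defined in 3.5.1 from the end of the 3-month blanking period (fixed time since PVI) to the 12-month visit.* This carries over the symptom pattern and the 30-second threshold.
2. Refer to the same definition in 3.11.1 where clinical success is used.
3. Word the recurrence bullet in 3.5.1 to cover any atrial arrhythmia, as the endpoint does. Otherwise the cross-reference would write an AF-only rule into success, while the CLOSE figure is quoted for AF, atrial tachycardia and flutter.
4. Report AF seen only during blanking separately, as early recurrence.
5. Keep the end of blanking independent of the visit date, and reconcile the visit schedules in 3.7 and 3.8.

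The definition changes are wording only: they need no new patients or treatment changes. Step 3 may lower the measured success rate relative to an AF-only count, but that is what the named endpoint already implies. The text may have to pass through the amendment procedure in 5.3.

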3. METHODS

3.1 Study design

Single-arm, international, multicenter, prospective study.

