3.11.2 Statistical methods

All applicable statistical tests will be 2-sided and will be performed using a 5% significance level. Continuous variables will be reported as mean \pm standard deviation, or median (range or interquartile range if data are skewed) if not normally distributed; these variables will be compared using Student's t-test if normally distributed or Mann-Whitney U test if not normally distributed. Categorical variables will be expressed as total number (percentage) and will be compared by chi-squared test. For the primary endpoint, survival free from atrial arrhythmia, we will use the Kaplan-Meier survival analysis. A multivariable Cox proportional hazards model will be performed to investigate the effects of baseline characteristics in predicting ablation results, an adjustment will also be done by recruiting center. A receiver operating curve analysis will be performed to determine optimal cutoff LAWT values for predicting AF recurrence after ablation. All efforts will be done to limit missing data on outcome. Nevertheless, missing data will be reported on the final manuscript and, as much as possible, the reasons why data are missing will be documented. If missing, a simple imputation method will be applied and reported.

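### The primary endpoint is named for any atrial arrhythmia and for survival, but the event and success rules name only AF, and no rule says how a death is scored

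*Combined protocol and SAP*

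**What the plan says.** Section 3.5.1 names the endpoint: "The primary endpoint will be survival free of any atrial arrhythmia at 1-year follow-up". The definition beneath it concerns AF alone: "AF recurrence will be considered only after the 3-month" window has passed. A recurrence then counts in any of three ways: "whenever the patient refers clear symptoms of recurrence", AF on an ECG, or a Holter recording longer than 30 seconds.

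Section 3.7 defines a successful ablation as no symptoms suggestive of AF recurrence, "as well as the absence of documented AF in ECGs and/or Holter". It also schedules a 12-lead ECG and a 24-hour Holter at every follow-up appointment.

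Death is on the secondary list in section 3.5.2.2, introduced by "The following procedure-related complications will be collected". It is not mentioned in 3.5.1 or 3.7.

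Section 3.11.2 gives the analysis: "For the primary endpoint, survival free from atrial arrhythmia, we will use the Kaplan-Meier survival analysis". It has no censoring or competing-event rule. For missing outcomes it says: "If missing, a simple imputation method will be applied and reported".

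The design in section 3.1 is "Single-arm, international, multicenter, prospective study". The comparator in section 3.11.1 is therefore an external one, the CLOSE protocol. The Introduction reports its result as 91.3% free from AF, AT and AFL at 12 months.

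**The concern.** The name of the endpoint and the rules that would be used to score it disagree in two places.

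The first is the arrhythmia. The name covers any atrial arrhythmia, and the benchmark covers AF, AT and AFL, but the rules name AF. Under the rules as written, AT or flutter documented in a patient without qualifying symptoms is not an event.

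The second is death. The name speaks of survival, but neither rule mentions death. A patient who dies without recurrence could be scored as a success, censored, imputed or counted as a failure, and the text does not choose.

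The trial has no concurrent control. In a two-arm trial an incomplete event rule would apply to both arms. Here it applies only to the new protocol, while the benchmark keeps its own definition. The non-inferiority conclusion in section 3.11.1 rests on this one rate.

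**Working it through.** **1. The rules applied to four patients.**

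| Patient | Endpoint as named (3.5.1) | Event and success rules (3.5.1, 3.7), literally |
|---|---|---|
| Asymptomatic flutter on Holter, month 6 | failure | no AF, so not an event |
| Flutter with clear palpitations, month 6 | failure | failure, by the symptom criterion |
| Death on day 25 | failure, if survival is taken at its word | no AF after month 3: success, or censored before any event can count |
| Death at month 8 in sinus rhythm | failure, on the same reading | success, or censored at month 8 |

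**2. The plan's own figure.** Section 3.11.1 gives n = 106 for 90% power, a one-sided 95% limit and a 10% margin, with 10% drop-out included. It states no assumed success rate. Using 91.3% from the Introduction, the null rate is 0.913 − 0.10 = 0.813 and

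n = (1.645·√(0.813·0.187) + 1.282·√(0.913·0.087))² / 0.10² = (0.641 + 0.361)² / 0.01 = 100.5, so 101.

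With drop-out, 101/0.9 = 112.2, so 113. The stated 106 is not reproduced from these inputs. The present point does not depend on that; both 106 and 95 (106 × 0.9) are used below.

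**3. Decision rule.** Non-inferiority is claimed if the exact (Clopper-Pearson) one-sided 95% lower limit exceeds 81.3%.
- n = 106: at least 94 successes are needed (94/106 gives 82.3%; 93/106 gives 81.2%).
- n = 95: at least 84 successes are needed (84/95 gives 81.6%; 83/95 gives 80.3%).

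The crude proportion stands in for the Kaplan-Meier estimate.

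**4. False non-inferiority.** Set the true success rate for the endpoint as named at the margin, 0.813. If a proportion u of patients are failures that the rules do not count, the observed success rate is 0.813 + u, and

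P(false claim) = P(X ≥ c), X ~ Binomial(n, 0.813 + u), with c = 94 or 84.

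| Uncounted failures | u (assumed) | n = 106 | n = 95 |
|---|---|---|---|
| None | 0 | 2.9% | 4.4% |
| AT/AFL | 1% | 5.0% | 7.1% |
| AT/AFL | 3% | 13.2% | 16.8% |
| AT/AFL | 5% | 29.2% | 33.6% |
| Deaths scored as successes | 0.3% to 1% | 3.4% to 5.0% | 5.1% to 7.1% |

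If deaths are censored instead, the observed rate is 0.813/(1 − u). At u = 1% this gives 4.5% (n = 106) and 6.6% (n = 95). The documents give neither an AT/AFL rate nor a 1-year mortality, so every non-zero u is an assumption.

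**5. A good result.** Take 97/106 event-free, which is 91.5% with a lower limit of 85.7%. Counting 1, 2 or 3 deaths as failures gives 90.6% (84.5%), 89.6% (83.4%) and 88.7% (82.3%). All stay above 81.3%. Each reclassified patient moves the rate by 1/106 = 0.9 points.

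Section 3.11.1 also gives a limit of −0.05, which conflicts with the 10% margin. At 91.3% − 5% = 86.3%, this example fails even with no deaths.

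**The case against.** The strongest reply is that the name governs. Survival free of any atrial arrhythmia already covers AT, flutter and death, and the AF wording is loose drafting that an analyst would read sensibly. That reading is open, and the documents do not rule it out. But it needs the name to override the only written event rule, and nothing says that it does.

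The symptom criterion also counts against the concern. Clear palpitations count without a tracing, so some AT and flutter is caught, and some symptoms that are not arrhythmia may be counted as failures. This narrows the gap to documented AT/AFL without qualifying symptoms.

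On death, the objections largely stand. Three stronger claims are tempting and should not be made:
- **That the plan scores a death as a success.** It says nothing. Success, censoring, the unspecified imputation and failure are all open.
- **That deaths bias the comparison with the reference.** The documents do not say how the reference treated deaths. If it ignored them, counting them only here would make the comparison slightly harder for the new protocol.
- **That deaths would be hidden.** Death is the first complication listed in 3.5.2.2, and the timeline in 3.8 records adverse events and termination to month 12.

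A reader might also infer from the ECG and/or Holter wording in 3.7 that a clean ECG alone is enough for success. The documents do not support this. Both tests are scheduled at every visit, and the natural meaning is that AF on either tracing is a failure, as in 3.5.1. A skipped Holter is missing data, which 3.11.2 addresses, if only in outline.

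**Conclusion.** The point holds as a contradiction between the endpoint's name and its scoring rules, together with a missing rule for death. It should be settled before results are seen.

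The AF-only wording is the main issue because both sides of the mismatch are on the page: AF in the rules, AF/AT/AFL in the benchmark. Read literally, it favours non-inferiority. If 3% of patients had uncounted AT/AFL, a false claim would occur in 13.2% of trials at n = 106 and 16.8% at n = 95, against 2.9% and 4.4% under a complete rule.

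The death gap is real but small: at most 5.0% (n = 106) or 7.1% (n = 95) at 1% mortality. Leaving deaths out can only raise the rate relative to an endpoint in which death is a failure. Whether it also tilts the comparison with the reference is unknown.

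These sizes assume a fixed 91.3% reference, the 10% margin, an exact one-sided 95% limit, and a true rate exactly at the margin. A result well clear of the margin would survive a few reclassified patients.

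**What to change.** - **Sections 3.5.1 and 3.7:** define the event as documented AF, AT or AFL after month 3, and keep the existing symptom criterion. Use the same list in both sections.
- **Section 3.5.1:** state that death from any cause up to 12 months, including in the first 3 months, is a primary-endpoint event on its date. The 3-month exemption then applies to arrhythmia only.
- **Section 3.7:** add being alive to the definition of success, and state that arrhythmia on either the ECG or the Holter is a failure.
- **Section 3.11.2:** add a sensitivity analysis of recurrence alone, with death as a competing event. This shows the result on a recurrence-only basis, in case the reference did not count deaths.

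Two changes should be avoided. Wording that refers to both the ECG and the Holter could be read as failure only when both are positive. Censoring patients without a 12-month Holter at their last completed Holter could erase a recurrence already seen on an ECG.

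The cost is a few sentences and one extra analysis. The success rate may fall by about 0.9 points for each death or each AT/AFL case that would otherwise go uncounted.

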3.8 Study timeline

PROCEDURE \ VISIT	Enrollment	Baseline	Ablation	1 month	6 months	12 months
Eligibility screen	✓					
Informed consent	✓					
Demographic Data		✓				
Medical History		✓				
Medication		✓		✓	✓	✓
NYHA Class		✓		✓	✓	✓
12-lead ECG		✓		✓	✓	✓
24-h Holter		(*)		✓	✓	✓
TTE		✓				✓
TOE			✓			
Allocation						
Ablation data			✓			
Protocol Deviation	✓ (*)	✓ (*)	✓ (*)	✓ (*)	✓ (*)	✓ (*)
Adverse event	✓ (*)	✓ (*)	✓ (*)	✓ (*)	✓ (*)	✓ (*)
Termination	✓ (*)	✓ (*)	✓ (*)	✓ (*)	✓ (*)	✓ (*)

3.9 Recruitment and agenda

All participant centers are tertiary referral centers for AF ablation within their health care network. All patients who give consent for participation and fulfill the inclusion eligibility criteria will be consecutively enrolled. First patient will be included after approval of the protocol by ethics committee. We expect to include all the patients within a year period. The

12-month follow-up information of the last included patient should be available approximately 2 years after the first inclusion.

3.10 Document and data control

The principal investigator or delegate is responsible of the data collection on the electronic Case Report Forms (eCRFs). This eCRFs will be introduced using an electronic clinical research data capture (eCRD) platform developed by the contract research organization (CRO) Xolomon SL. The principal investigator will review all the data on the eCRFs and will sign to verify he has reviewed the data collected. Original anonymized paper support forms will be stored in a secure place and manner at each participating center. Anonymization codes will be stored in a safely manner by the local principal investigator. Access to the online study data (eCRFs) will be restricted through passwords. In addition, center coordinators will only have access to their own center's data. Paper files will be physically stored until 5 years after the completion of the study.

3.10.1 Traceability of documents and data

The investigator shall ensure accuracy, completeness, legibility and timeliness of the data reported to the principal investigator on the eCRFs and in all required reports. When copies of the original source document as well as print outs of original electronic source documents are retained, these shall be signed and dated by a member of the investigational site team with a statement that it is a true reproduction of the original source document.

